APPENDIX D-1: BLOOD BANKING COLLECTION FORM (OPTIONAL)

Patient MRN (COH Only):

Patient Initials (F, M, L):

Institution:

Sample Collection:

1. A 10 mL baseline sample should be collected from consenting patients.
2. Label each sample with the participants' initials, study ID number, date of collection, and sample collection time.
3. A green top heparin OR a lavender top K+EDTA tube should be used for collecting the sample.
4. After collection, gently invert the tube several times (at least 4 times) and place on ice.
5. **For COH-Duarte Campus:**
 - Samples placed on ice may be taken immediately to CICSL in Shapiro (room 1042) on the day of collection; arrangements should be made ahead of time with [name] (email: [contact] or [name]). Samples will then be frozen at -60°C to -90°C at CICSL.
6. **For COH Community Practices:**
 - Store samples in a -60°C to -90°C freezer. Frozen -60°C to -90°C samples should be taken on dry ice to the Clinical Immunobiology Correlative Studies Laboratory (CICSL) in Shapiro (room 1042).
7. **For Non-COH sites:**
 - Store in a -60°C to -90°C freezer until shipment. Refer to [Appendix D-2](#) for shipping details.

Sample #	Schedule	Collected Volume	Tube Type Used (Select One)	Time of Collection	Date of Collection
1	Day 1: Prior to protocol therapy	_____ mL	Sodium heparin Lithium heparin K ₂ EDTA K ₃ EDTA	____:____ AM/ PM	____/____/____

A copy of this form should be maintained by the institution and a copy should accompany the sample to CICSL.

CRA/Study Coordinator:

Contact Number:

CRA/Study Coordinator Signature:

Date:

APPENDIX E: RIBOCICLIB PILL DIARY

Study Accession #:	Patient Initials (F, M, L):
Institution:	Cycle #:

Ribociclib should be taken **once every day for 21 days by mouth**. Ribociclib should be taken **at approximately the same time each day**. If you miss or vomit a dose do not make up the missed/vomited dose that day; instead take the ribociclib dose the next day at the regularly scheduled time. Ribociclib pills should be swallowed whole.

Record all side effects, missed ribociclib doses, supplements and other medication you are taking in the Pill Diary.

Bring the study drug bottle to every clinic visit to show _____. At the **end of each cycle**, please return this diary and study drug bottle to _____.

How to fill the Pill Diary (Example Only)

To be filled in by the institution

Cycle #: 1 Cycle Start Date: 9/7/2016

Ribociclib Dose: 125 mg/ day Take: 1 pill per day

To be filled in by the patient			# of pills taken	Comments
Day	Date	Time		
1	9/7/16	8:20 am/pm	1	Nausea. Muscle pain.
2	9/8/16	8:20 am/pm	1	Vomited the pill but did not take an extra pill today.

Cycle #: _____ Cycle Start Date: _____

Ribociclib Dose: _____ mg/ day Take: _____ pill per day

Week 1			# of pills taken	Comments
Day	Date	Time		Side effects, supplements, other medication, missed doses
1		____:____ am/pm		
2		____:____ am/pm		
3		____:____ am/pm		
4		____:____ am/pm		
5		____:____ am/pm		
6		____:____ am/pm		
7		____:____ am/pm		

Ribociclib Dose: _____ mg/ day Take: 1 pill per day

Week 2			# of pills taken	Comments
Day	Date	Time		Side effects, supplements, other medication, missed doses
8		____:____ am/pm		
9		____:____ am/pm		
10		____:____ am/pm		
11		____:____ am/pm		

12		____:____ am/pm		
13		____:____ am/pm		
14		____:____ am/pm		

Ribociclib Dose: _____ mg/ day Take: 1 pill per day

Week 3			# of pills taken	Comments
Day	Date	Time		Side effects, supplements, other medication, missed doses
15		____:____ am/pm		
16		____:____ am/pm		
17		____:____ am/pm		
18		____:____ am/pm		
19		____:____ am/pm		
20		____:____ am/pm		
21		____:____ am/pm		

Rest Week

Week 4			# of pills taken	Comments
Day	Date	Time		Side effects, supplements, other medication, missed doses
22				
23				
24				

Do not take Ribociclib this week.

25		
26		
27		
28		

Participant Signature (please sign at the end of the cycle when submitting your diary)

Date:

Nurse Signature

Date:

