The relationship between plasma trough and percent drop in neutrophil and platelet counts will be analyzed using linear models methods.

Abbreviated Eligibility Criteria:

Inclusion Criteria

- Hormone receptor positive metastatic breast cancer.
- First or second line endocrine therapy for metastatic disease. One prior line of chemotherapy for metastatic disease is allowed.
- Age: ≥ 70 years and life expectancy > 6 months
- Measurable disease per RECIST (1.1), or bone-only lytic or mixed lytic and blastic lesions that would be accurately assessed by means of computed tomography (CT) or magnetic resonance imaging (MRI).
- The ability to swallow and retain oral medication
- Resolution of all acute toxic effects of prior therapy or surgical procedures to CTCAE Grade ≤ 1 (except alopecia)

Exclusion Criteria

- Untreated brain metastases or symptomatic visceral spread at risk for life-threatening complications
- Concomitant CYP3A strong inhibitors or inducers
- Prior therapy with a CDK inhibitor

Investigational Product Dosage and Administration:

Ribociclib: Administered orally with food on Days 1-21 in each 28-day cycle. Starting dose: 600mg/day.
Aromatase inhibitor: Administered per treating investigator's discretion during each 28-day cycle; dosing should follow the package insert guidelines.

Clinical Observations and Tests to be Performed:

Clinical Observations/ Tests/ Questionnaires: medical history and demographics, physical exams, vital signs, performance status, routine laboratory tests, pill diary assessment, AE assessment, disease assessment, geriatric assessment, Was It Worth It Questionnaire assessment, Overall Treatment Utility assessment. Participants will be followed for survival.

Correlative Biology Studies: From participants who consent to research blood sample collection, a baseline sample of blood will be collected for future studies.

TABLE OF CONTENTS

SECTION	PAGE
Experimental Design Schema	3
Protocol Synopsis.....	4
Table of Contents	8
List of Tables and Figures.....	10
Abbreviations.....	11
1. Goals and Objectives (Scientific Aims).....	12
2. Background	12
2.1. Introduction/Rationale for Development	12
2.2. Rationale for Studying Cancer Therapy in Older Adults.....	12
2.3. Factors Other than Chronological Age that Impact Drug Tolerance	13
2.4. Ribociclib	14
2.5. Overview and Rationale of Study Design	15
3. Participant Eligibility Criteria	17
3.1. Inclusion Criteria	157
3.2. Exclusion Criteria.....	18

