5.3. Treatment Plan and Agent Administration

Table 5.3: Treatment regimen

Agent	Starting Dose	Frequency of Administration	Route of Administration
Ribociclib	600 mg/ day	Once daily on Days 1-21 of each 28-day cycle	Orally
Aromatase inhibitor	Per package insert	Per treating investigator's discretion during each 28-day cycle	Per package insert

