6.2. Dose Modifications/ Delays

6.2.1. General Information:

1. The cycle length will remain 28 days (\pm 2 days) despite a delay in initiating ribociclib on Day 1; endocrine therapy may continue to be administered per the preplanned schedule.
2. Dose holds/reductions of endocrine therapy will occur per treating investigator's discretion.
3. See [Table 6.2.1](#) for criteria to dose modify ribociclib. Dose reductions are as follows:

Table 6.2.1: Ribociclib dose levels

Dose Level	Dose
Starting dose	600 mg/day
First dose reduction	400 mg/day
Second dose reduction	200 mg/day
Third dose reduction	discontinue protocol therapy

Table 6.2.2a: Ribociclib Dose Modification and Management - Hematologic Toxicities

CTCAE v 4.0 Grade	Ribociclib Dose Modifications For Hematologic Toxicities
Grade ≤ 2	Maintain treatment.
Grade 3 (Except febrile neutropenia OR lymphopenia associated with clinical events)	Hold ribociclib until recovery to Grade ≤2. Consider repeating complete blood count monitoring one week later. 
 • Upon recovery Grade ≤2 within 28 days resume therapy at the pre-hold dose. • Permanently discontinue protocol therapy if the toxicity persists for > 28 days.
Grade 3 ANC (<1000 to 500/mm³) + Fever (≥38.5°C) OR Grade 3 ANC + infection	Hold ribociclib until recovery to Grade ≤2 ($\geq 1000/\text{mm}^3$). 
 • Upon recovery Grade ≤2 within 28 days resume therapy at the next lower dose. • Permanently discontinue protocol therapy if the toxicity persists for > 28 days.
Grade 4 ANC <500/mm³ (Except lymphopenia associated with clinical events)	Hold ribociclib until recovery to Grade ≤2. 
 • Upon recovery Grade ≤2 within 28 days resume therapy at the next lower dose. • Permanently discontinue protocol therapy if the toxicity persists for > 28 days.

Table 6.2.2b: Ribociclib Dose Modification and Management- Non-Hematologic Toxicities

	CTCAE v 4.0 Grade	Dose Modifications For Non-Hematologic Toxicities
RELATED to Ribociclib	Grade ≤ 2	Maintain treatment.
	Grade ≥ 3	
Hold ribociclib until recovery to Grade ≤1 or baseline.
 
 Upon recovery to Grade ≤1 or baseline within 28 days resume therapy at the next lower dose if medically appropriate at the discretion of the treating physician. Permanently discontinue protocol therapy if the toxicity persists for > 28 days

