8.1.6. Formulation

Ribociclib is supplied as a 600 mg, 400 mg, or 200 mg doses in assorted blister packs. Each film-coated contains 200 mg of ribociclib free base. Ribociclib is supplied as a light greyish violet, round tablet, curved with beveled edge, debossed with “RIC” on one side and “NVR” on the other. Inactive ingredients present in the tablet include: colloidal silicon dioxide, crospovidone, hydroxypropylcellulose, magnesium stearate, and microcrystalline cellulose.

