13.1.6 Exploratory Endpoints

1. Adherent to ribociclib will be defined as taking 19/21 pills (90%) of their dose of ribociclib.
2. Toxicity Risk Score
3. WIWI response
4. OTU response

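### Appendix E pre-prints one pill per day over Weeks 2 and 3 of the pill diary, which is wrong at the 600 mg starting dose (3 tablets) and at the 400 mg first reduction (2 tablets)

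*Combined protocol and SAP*

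**What the plan says.** Ribociclib is given as "Once daily on Days 1-21 of each 28-day cycle" (Table 5.3), and the synopsis states "Starting dose: 600mg/day". The table headed "Table 6.2.1: Ribociclib dose levels" then steps down to 400 and 200 mg/day before protocol therapy is discontinued. On tablet strength, Section 8.1.6 says "Each film-coated contains 200 mg of ribociclib free base". The same section describes blister packs for daily doses of 600, 400 and 200 mg. It describes no tablet stronger than 200 mg.

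The diary in Appendix E has one block per week.

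- Week 1 leaves both fields open: "Ribociclib Dose: _____ mg/ day Take: _____ pill per day".
- Weeks 2 and 3 leave the milligrams open but print the count: "Ribociclib Dose: _____ mg/ day Take: 1 pill per day".
- The worked example at the top reads "Ribociclib Dose: 125 mg/ day Take: 1 pill per day" and enters 1 in the pills column on both sample days.

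The exploratory adherence endpoint, in the synopsis and in Section 13.1.6, is defined as "taking 19/21 pills (90%) of their dose of ribociclib".

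**The concern.** The diary is the written instruction that the patient takes home, and Section 5.3.1 makes it the tool for assessing compliance. Every participant starts at 600 mg/day. A form completed correctly by the site at that dose would therefore show 600 mg/day and 1 pill on the same line in Weeks 2 and 3, after a Week 1 header showing 3. The two entries contradict each other, and nothing else on the form says which one governs.

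The example gives no help. Its dose, 125 mg/day, is not a level in this protocol and cannot be made up from 200 mg tablets.

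What is at stake is correct dosing of an individual older patient for up to two weeks of a cycle, and a clean record of what was taken. The point does not depend on any effect on the trial's estimates.

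**Working it through.** **Inputs.** Tablet strength is 200 mg (Section 8.1.6). Dose levels are 600, 400 and 200 mg/day (Table 6.2.1). There are 21 dosing days per cycle (Table 5.3), of which Days 8 to 21, 14 days, fall under the Week 2 and Week 3 headers. The printed count is 1 (Appendix E).

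**Step 1: where the printed figure can be reproduced.** Tablets per day = prescribed mg/day ÷ 200 mg. Fraction of the daily dose delivered by one tablet = 200 ÷ prescribed mg/day.

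| Dose level | Tablets per day | Tablets per 21 days | One pill as share of daily dose | Printed count correct? |
|---|---|---|---|---|
| 600 mg | 600/200 = 3 | 63 | 200/600 = 33% | No |
| 400 mg | 400/200 = 2 | 42 | 200/400 = 50% | No |
| 200 mg | 200/200 = 1 | 21 | 200/200 = 100% | Yes |

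The printed 1 is reproduced only at the last level before discontinuation.

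**Step 2: can pill mean daily dose?** That reading would make 1 correct at every level. The diary does not support it: each daily row has a column for the number of pills taken, and the Week 1 header leaves the count open, which would be unnecessary if the answer were always 1.

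**Step 3: largest effect within one cycle (illustration only).** Suppose Week 1 is taken correctly, the header is then followed for all 14 remaining days, and nobody corrects it.

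- At 600 mg: (7 × 600 + 14 × 200) / (21 × 600) = 7,000/12,600 = 56%.
- At 400 mg: (7 × 400 + 14 × 200) / (21 × 400) = 5,600/8,400 = 67%.

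These describe one hypothetical patient. The documents give no basis for a frequency.

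**Step 4: the adherence wording.** 19/21 = 90.5%, which agrees with the stated 90% when the unit is a daily dose, and there are 21 daily doses per cycle at every level. Counted in tablets at 600 mg, 19/63 = 30%, which contradicts the 90% in the same definition. The threshold is sound in daily doses, and only the unit word is loose.

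**The case against.** The strongest reply is that this is a slip on a form and that the protocol surrounds it with controls. Much of that stands.

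- Staff write the prescribed mg/day on the same header line, and a new Week 1 count is written every cycle.
- Drug is supplied in packs by daily dose.
- The diary has a daily pill column and a nurse signature, and it is returned with the bottle each cycle. Patients also bring the bottle to clinic visits.
- In Cycles 1 and 2 there are Day 8 and Day 15 contacts. Section 10.2 has patients wait for the blood draw before taking that day's dose, which is a natural moment to discuss it.

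These controls lower the risk but do not correct the text.

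- Section 8.1.8 allows repackaging, and the diary speaks of a bottle, so a patient may not hold the dose-specific pack.
- As extracted, Table 11.0 marks the diary on Day 1 of each cycle and off treatment, not on Day 8 or Day 15. From Cycle 3 it schedules only Day 1 visits within the cycle.
- Under footnote t of that table, late return of the diary does not count as a deviation.
- The accountability record in Section 8.1.11 covers inventory and disposition. It does not specify a count of each patient's tablets.

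It is also fair that the 125 mg block is labelled as an example and is not a dosing instruction. It merits correction but little weight.

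Three stronger readings are tempting, and the documents do not support them.

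1. **That toxicity, dose-reduction or trough results will be biased.** A reader might note that the Day 15 trough follows a full Week 2, and that 7 days is 168/32 = 5.25 of the half-lives given in Section 8.1.4. But this requires patients to follow the printed count over the written milligrams, and no rate for that is given.
2. **That the adherence endpoint accepts 30% of the dose.** The 90% in the definition, with 21 daily doses, rules this out as the intended meaning.
3. **That the handling of protocol-directed hold days is part of the same error.** The definition is silent on holds, but whether hold days count in the denominator is a separate convention for an exploratory rate. Simply removing them leaves adherence undefined (0/0) in a cycle held throughout Days 1 to 21.

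**Conclusion.** The Week 2 and Week 3 headers are wrong as written at two of the three dose levels, including the one on which every participant starts. The size per day is exact: a patient who obeyed the header would take one third of the prescribed dose at 600 mg and one half at 400 mg. This rests only on the 200 mg tablet strength, the dose table and the ordinary meaning of pill, which the diary's own column supports.

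How often it would happen is unknown. The 56% and 67% cycle figures illustrate the uncorrected case and are not estimates of exposure in the trial. No effect on the primary endpoint, the sample size or the analysis methods is shown. The correction is warranted because this is a dosing instruction held by the patient and no other text overrides it.

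**What to change.** In Appendix E, replace the printed 1 in the Week 2 and Week 3 headers with a blank for the site to complete (3, 2 or 1 tablets), as Week 1 already does. Change the worked example to 600 mg/day and 3 pills per day, with 3 in both sample rows.

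As an optional wording correction, change the adherence unit in the synopsis and in Section 13.1.6 from pills to daily doses, keeping 19 of 21 and 90%. If the team also wants a rule for hold days, it should be decided separately, including what happens when a whole cycle is held.

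The cost is one reissued patient form and, if taken up, one word changed in two places, all under a single IRB-approved amendment. These changes need no additional data and no change to the analysis.

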APPENDIX F-2: GERIATRIC ASSESSMENT SURVEY

Completed via touchscreen computer survey (preferable) or paper assessment forms. A PDF version formatted to collect information will be provided to participating sites.[27]

Patient Questionnaire

Responsible person name (Physician, Nurse, or CRA) _____
Assessment Period (as applicable to this study) Pre-treatment Cycle # End of Treatment

Patient Instructions: If you are unable to complete the questionnaire, a member of your health care team will assist you. Please do not have a family member complete the questionnaire for you.

Mark box with an "X", if form was not completed at specified timepoint and specify reason:

(Mark one with an X.) Patient refused Patient withdrew consent Not done
 Other, specify _____

(For assessment date, record approximate date form was to be completed.)

A. BACKGROUND INFORMATION

1. What is the highest grade you finished in school? (Mark one with an X.)

Less than 9 years of school Some college or technical school Post graduate education, but no higher degree
 Some high school (9-11 years) College degree graduate
 High school graduate, or GED Graduate degree I prefer not to answer

2. What is your marital status? (Mark one with an X.)

Married Divorced I prefer not to answer
 Domestic partnership Separated
 Widowed Never married

3. With whom do you live? (Mark all that apply with an X.)

Spouse / partner Parents/ parents-in-law
 Girlfriend / boyfriend Live alone
 Children aged 18 years or younger Others, specify: _____
 Children aged 18 years or older Other relative, specify: _____

4. What is your current employment status? (Mark one with an X.)

Employed ≥ 32 hours per week Unemployed
 Employed ≤ 32 hours per week Retired
 Homemaker Student full-time
 Disabled Student part-time
 On medical leave Other, specify: _____

5. How old are you? ____ years old

6. What is your race?

White Asian
 Black or African American Native Hawaiian or Other Pacific Islander
 Native Indian or Alaskan Native Unknown

7. What is your ethnicity?

Hispanic or Latino Non-Hispanic Unknown

B. DAILY ACTIVITIES*

PATIENT INSTRUCTIONS: Indicate your response by marking an X in one box per question.

1. Can you use the telephone...
 - Without help, including looking up and dialing
 - With some help (can answer phone or dial operator in an emergency, but need a special phone or help in getting the phone number or dialing)
 - Completely unable to use the telephone

2. Can you get to places out of walking distance...
 - Without help (can travel alone on busses, taxis, or drive your own car)
 - With some help (need someone to help you or go with you when traveling)
 - Completely unable to travel unless emergency arrangements are made for a specialized vehicle like an ambulance

3. Can you go shopping for groceries or clothes (assuming you have transportation) ...
 - Without help (taking care of all shopping needs yourself, assuming you have transportation)
 - With some help (need someone to go with you on all shopping trips)
 - Completely unable to do any shopping

4. Can you prepare your own meals...
 - Without help (plan and cook full meals yourself)
 - With some help (can prepare some things but unable to cook full meals yourself)
 - Completely unable to prepare any meals

5. Can you do your housework...
 - Without help (can clean floors, etc.)
 - With some help (can do light housework but need help with heavy work)
 - Completely unable to do any housework

6. Can you take your own medicines...
 - Without help (in the right doses at the right time)
 - With some help (able to take medicine if someone prepares it for you and/or reminds you to take it)
 - Completely unable to take your medicines

7. Can you handle your own money...
 - Without help (write checks, pay bills, etc.)
 - With some help (manage day-to-day buying but need help with managing your checkbook and paying your bills)
 - Completely unable to handle money

* OARS IADL [28]

C. PHYSICAL ACTIVITIES*

1. The following items are activities you might do during a typical day. Does your health limit you in these activities? (Mark an X in the box on each line that best reflects your situation.)

Activities	Limited a lot	Limited a little	Not limited at all
a. Vigorous activities such as: running, lifting heavy objects, participating in strenuous sports			
b. Moderate activities such as: moving a table, pushing a vacuum cleaner, bowling, or playing golf			
c. Lifting or carrying groceries			
d. Climbing several flights of stairs			
e. Climbing one flight of stairs			
f. Bending, kneeling, or stooping			
g. Walking more than a mile			
h. Walking several blocks			
i. Walking one block			
j. Bathing or dressing yourself			

* MOS, Physical Functioning Scale [29]

D. CURRENT HEALTH RATING*

Which one of the following phrases best describes you at this time? (Mark one with an X.)

- Normal, no complaints, no symptoms of disease
- Able to carry on normal activity, minor symptoms of disease
- Normal activity with effort, some symptoms of disease
- Care for self, unable to carry on normal activity or do active work
- Require occasional assistance but able to care for most of personal needs
- Require considerable assistance for personal care
- Disabled, require special care and assistance
- Severely disabled, require continuous nursing care

* Patient KPS[30]

E. FALLS

How many times have you fallen in the last 6 months?

F. YOUR HEALTH

1. Your General Health*

Patient Instructions: Do you have any of the following illnesses at the present time, and if so, how much does it interfere with your activities: **Not at all, Somewhat or A Great Deal?** (Mark an X in the box that best reflects your answer.)

If you have this illness:
How much does it interfere with your activities?

Illness	No	Yes	Not at all	A little	A great deal
a. Other cancers or leukemia			→		
b. Arthritis or rheumatism			→		
c. Glaucoma			→		
d. Emphysema or chronic bronchitis			→		
e. High blood pressure			→		
f. Heart disease			→		
g. Circulation trouble in arms or legs			→		
h. Diabetes			→		
i. Stomach or intestinal disorders			→		
j. Osteoporosis			→		
k. Chronic liver or kidney disease			→		
l. Stroke			→		
m. Depression			→		

* OARS IADL[28]

2. How is your eyesight (with glasses or contacts)? (Mark one with an X.)

- Excellent
- Good
- Fair
- Poor
- Totally blind

If fair, poor, or totally blind, how much does it interfere with your activities?

- Not at all
- Somewhat
- A great deal

3. How is your hearing (with a hearing aid, if needed)? (Mark one with an X.)

- Excellent

- 2 Good
- 3 Fair
- 4 Poor
- 5 Totally deaf

If fair, poor, or totally deaf, how much does it interfere with your activities?

- Not at all
- Somewhat
- A great deal

4. Do you have any other physical problems or illnesses (other than listed in questions 1-4) at the present time that seriously affect your health?

- No

- Yes, specify:

If yes, how much does this interfere with your activities? (Mark one with an X.)

- Not at all
- Somewhat
- A great deal

* OARS IADL[28]

G. NUTRITIONAL STATUS

1. Have you lost weight involuntarily over the past 6 months?

- No
- Yes

If yes, how much?

pounds

2. What is your weight now?

pounds

3. What was your weight 6 months ago?

pounds

Notation for Study Build Team: If a medication form is being used for the main study, this medication form does not need to be included in the Patient Questionnaire.

How many medications (either prescribed or over-the-counter), herbs, or vitamins do you currently take?

Please list all prescribed or over-the-counter medicines, herbs, or vitamins you are currently taking (doses not necessary).

1.
2.
3.
4.
5.
6.

7.

8.

9.

10.

11.

12.

13.

14.

15.

H. HEALTH QUESTIONNAIRE*

INSTRUCTIONS: These questions are about how you have been feeling within the past month. Please mark an "X" in the box on each line that best reflects your situation.

How much of the time during the past two weeks:	All of the Time	Most of the Time	A Good Bit of the Time	Some of the Time	A Little of the Time	None of the Time
1. has your daily life been full of things that were interesting to you?						
2. did you feel depressed?						
3. have you felt loved and wanted?						
4. have you been a very nervous person?						
5. have you been in firm control of your behavior, thoughts, emotions, feelings?						
6. have you felt tense or high-strung?						
7. have you felt calm and peaceful?						
8. have you felt emotionally stable?						
9. have you felt downhearted and blue?						

10. have you felt restless, fidgety, or impatient?						
11. have you been moody, or brooded about things?						
12. have you felt cheerful, light-hearted?						
13. have you been in low or very low spirits?						
14. were you a happy person?						
15. did you feel you had nothing to look forward to?						
16. have you felt so down in the dumps that nothing could cheer you up?						
17. have you been anxious or worried?						

* MHI-17 [29]—

I. SOCIAL ACTIVITIES*

1. During the past 4 weeks, how much time has your physical health or emotional problems interfered with your social activities (like visiting with friends, relatives, etc.)?
 - All of the time
 - Most of the time
 - Some of the time
 - A little of the time
 - None of the time
2. Compared to your usual level of social activity, has your social activity during the past 6 months decreased, stayed the same, or increased because of a change in your physical or emotional condition?
 - Much less socially active than before
 - Somewhat less socially active than before
 - About as socially active as before
 - Somewhat more socially active as before
 - Much more socially active than before
3. Compared to others your age, are your social activities more or less limited because of your physical health or emotional problems?
 - Much more limited than others
 - Somewhat more limited than others
 - About the same as others
 - Somewhat less limited than others
 - Much less limited than others

* MOS, Social Activities [29]

J. SOCIAL SUPPORT*

INSTRUCTIONS: People sometimes look to others for companionship, assistance or other types of support. How often is each of the following kinds of support available to you if you need it? (Mark an X in the box on each line that best reflects your situation.)

	None of the Time	A Little of the Time	Some of the Time	Most of the Time	All of the Time
1. Someone to help you if you were confined to bed.					
2. Someone you can count on to listen to you when you need to talk.					
3. Someone to give you good advice about a crisis.					
4. Someone to take you to the doctor if needed.					
5. Someone to give you information to help you understand a situation.					
6. Someone to confide in or talk to about yourself or your problem.					
7. Someone to prepare your meals if you were unable to do it yourself.					
8. Someone whose advice you really want.					
9. Someone to help you with daily chores if you were sick.					
10. Someone to share your most private worries and fears with.					
11. Someone to turn to for suggestions about how to deal with a personal problem.					
12. Someone who understands your problems.					

* MOS Social Support Survey [31]

K. SPIRITUALITY/RELIGION

Directions: Please answer the following questions about your religious beliefs and/or involvement. (Please mark an "X" in the box on each line that best reflects your situation.)

1. How often do you attend church, synagogue, or other religious meetings?

- More than once per week
- Once a week
- A few times a month
- A few times a year
- Once a year or less
- Never

2. How often do you spend time in private religious activities, such as prayer, meditation, or Bible study?

- More than once a day
- Daily
- Two or more times per week
- Once a week
- A few times a month
- Rarely or never

The following section contains 3 statements about religious belief or experience. Please mark the extent to which each statement is true or not true for you.

3. In my life, I experience the presence of the Divine (i.e., God).
 - Definitely true of me
 - Tends to be true
 - Unsure
 - Tends *not* to be true
 - Definitely *not* true
4. My religious beliefs are what really lie behind my whole approach to life.
 - Definitely true of me
 - Tends to be true
 - Unsure
 - Tends *not* to be true
 - Definitely *not* true
5. I tried hard to carry my religion over into all other dealings in my life.
 - Definitely true of me
 - Tends to be true
 - Unsure
 - Tends *not* to be true
 - Definitely *not* true

*DUREL: Duke University ReligionIndex [32]

L. YOUR FEELINGS*

1. Do you often feel sad or depressed? No Yes

2. How would you describe your level of anxiety, on average? Please circle the number (0-10) best reflecting your response to the following that describes your feelings **during the past week, including today**.

0 1 2 3 4 5 6 7 8 9 10
No anxiety Anxiety as bad as
It can be

*Mahoney et al., 1994; LASA [33]

M. QUESTIONS CONCERNING THE QUESTIONNAIRE

1. Were there any questions difficult to understand? No Yes
If Yes, which questions were they?

For more information, contact the Office of the Vice President for Research and Economic Development at [contact] or [contact].

2. Was the time it took to answer all the questions too long, just right or too short?

- Too short → How long would you have liked the questionnaire to be? minutes
- Just right
- Too long → How long would you have liked the questionnaire to be? minutes

Which items would you remove?

1. **What is the primary purpose of the proposed legislation?**

3 Did you find any of the questions upsetting? No Yes

If Yes, which questions were they?

10. *What is the primary purpose of the following statement?*

Could you tell me why they were upsetting?

4. Do you think the questionnaire left out any questions that were important to ask?

Thank you for your participation.

